6.12 Communication with participants

Trial participants will be asked if they want to be sent a regular newsletter via email to update them on study progress. This will also be uploaded to the study website. Participants will also be asked if they want to be sent a plain English summary of the findings.

6.13 End of trial

Participants end their involvement with the trial when their last planned interaction with the study is complete (or efforts to complete this have been unsuccessful), in this case the 52 week questionnaire, or when they have discontinued their participation in the study.

The end of trial will be when the last participant has completed their involvement with the trial, all data collection is complete and any data queries have been resolved, the database has been locked, and subsequent planned data analyses have been completed.

6.14 Trial stopping rules

The trial may be prematurely discontinued by the Sponsor, CI, Regulatory Authority or Funder based on new safety information or for other reasons given by the DMC, regulatory authority or ethics committee concerned.

The trial may also be prematurely discontinued due to lack of recruitment or upon advice from the TSC, who will advise on whether to continue or discontinue the trial and make a recommendation to the Funder.

If the trial is prematurely discontinued, no new participants will be recruited, and a decision on data collection on active participants will be made in discussion with the TSC/DMC and Sponsor.

6.15 Integrated qualitative research

6.15.1 Aims and Objectives

The qualitative study will examine the acceptability of EMDR for depression, the application of EMDR for depression compared with PTSD, further explore mechanisms and identify possible causes of differing responses that could explain the trial results. Specific objectives are detailed in section 4.5. It will entail conducting in-depth interviews with trial participants, individuals who are approached to

take part in the trial but decline to so, and the EMDR trainers, supervisors and therapists involved in the trial.

The qualitative researcher will be employed by Bristol Trials Centre and will conduct the qualitative interviews. They will conduct the qualitative analysis in collaboration with the qualitative lead, also based at the University of Bristol.

6.15.2 Consent

Participants recruited to the main trial will be asked to consent to being approached for interview as part of their baseline consent. The possibility of being interviewed as part of the trial will be mentioned in the main study PIL. The aim will be to interview a sample of participants shortly after they have completed their primary outcome measures for the trial at 26-weeks post-randomisation. The qualitative researcher employed on the trial will be informed by the trial team who has completed their 26 week follow up. The qualitative researcher will email or post participants sampled for interview an information leaflet about the qualitative study. The researcher will then contact them two weeks later, by telephone, to explain more about the interview, answer any questions and, if they agree, arrange a convenient time and preferred method (e.g., phone/video) to conduct the interview.

During the pilot for the main trial, short telephone interviews will be held with up to 10 individuals who were invited to take part in the trial but decline to do so. These 'decliners' will be individuals who have received a letter inviting them take part in the trial, having been identified via systematic searches of GP practice records of depression. The trial invite letter will be accompanied by a reply slip, which the individual will be asked to complete and return (or complete online), indicating whether they are willing to be contacted by a researcher to discuss participation in the trial. If they do not want to take part, they will be asked to indicate this and complete a short questionnaire. This questionnaire will ask for their age, gender and reason(s) for declining participation, using a series of closed responses and one open 'other' category. These items will be based on previous research [61, 62]. The reply slip (or online form) will also ask individuals whether they would be willing to take part in a short telephone interview to discuss their reasons for declining in more detail. The qualitative researcher will approach a purposeful sample of decliners, explain more about the interview, answer any questions, and, if they agree, arrange a convenient time and preferred method (e.g., phone/video) to conduct the interview. The aim will be to interview decliners within a month of them returning the reply slip. This will provide another standpoint from which to assess the acceptability of EMDR and indicate ways to maximise recruitment.

Therapists, clinical supervisors, and EMDR trainers will be informed about the interviews through their respective information leaflets, which will be provided ahead of arranging an interview. When the interviews are due to be held, the qualitative researcher will telephone the therapists, supervisors and trainers to answer any questions they might have and to arrange an interview.

As all of the interviews will be conducted remotely, verbal consent to participate will be taken. It will be obtained by the qualitative researcher immediately prior to interview and will be audio recorded. This will involve the researcher reading out standard consent form statements and, if appropriate, the participant verbally agreeing to them. The researcher will complete the consent form on behalf of the participant, sign and date it, and email a copy of the completed consent form to the individual. The audio recorded excerpts will be retained for auditing purposes in line with trial archiving policies.

6.15.3 The interviews

To examine the application of EMDR for depression, prior to training trial therapists, or shortly thereafter, a paired in-depth interview will be held with the EMDR trainers to understand how the DeprEnd (EMDR for depression) protocol [8] is tailored EMDR to depression management, and what they think are the similarities and differences in the application of EMDR to depression compared with PTSD, in terms of mechanisms of actions (particularly in relation to the WM hypothesis), and events worked on. In addition, trial therapists will be interviewed on a one-to-one basis within approximately two weeks of completing training, to explore the same issues, and to assess their expectations of delivering EMDR in the trial. The trainers' interview will last up to an hour. The therapist interviews will last up to 30 minutes.

To further examine the application of EMDR and its mechanisms, and to explore its acceptability as a depression treatment, in-depth interviews will also be held with participants within a month of them completing their primary (trial) outcomes (with, depending on data saturation, up to 20 intervention (including those who do not complete therapy) and 10 UC), and with all trial therapists and supervisors once therapy is completed at their trial site. These interviews will last about an hour and will explore interviewees' views and experiences of UC and EMDR for depression, and their views on how EMDR affects the intensities of memories, self-beliefs and symptoms linked to distressing events. Having supported the therapists during the trial, supervisors will also be asked what they think are the similarities and differences in the application of EMDR to depression compared with PTSD.

'Decliners' and trial participants will be purposefully sampled across sites on the basis of gender, ethnicity, age and socio-economic background. Trial participants will also be sampled to achieve maximum variation in relation to baseline antidepressant use and depression severity, change in BDI-II score and, for the EMDR group, treatment adherence. All interviews will be held by telephone or videocall to encourage participation, and because it is now acknowledged that remote interviews can result in data of the same quality and value, as those held in person [63]. Consent will be taken immediately prior to interview as detailed in section 6.15.2.

Topic guides will be used to ensure consistency across the interviews. For the trial participants, there will be two guides: one to use with individuals allocated to EMDR plus usual care, and one to use with individuals allocated to receive usual care only. Guides will be developed in parallel to ensure areas common to different groups of interviewees are included in each guide. This will aid triangulation of trainers', supervisors', therapists', and patients' accounts during the analysis phase. Trainers, therapists and supervisors will be asked to complete a brief demographic questionnaire after their interview, so that the sample can be described when disseminating results.

Interviews will be audio recorded, transcribed verbatim and anonymised. Trial participants will be given a £20 voucher for taking part in an interview. The supervisors, therapists, trainers and decliners will not be given a voucher or paid for taking part in an interview.

6.15.4 Safeguarding during qualitative research

We will ensure that participants are not subjected to undue distress during the qualitative component of the trial. To mitigate this, the GCP-trained interviewer will be experienced in sensitive interviewing, will adhere to the safety working instructions and will conduct the interviews according

to trauma-informed research guidelines to ensure participants feel safe and empowered throughout the research process [64]. The interview will only continue if participants are happy to proceed and engage with the interview topic. If the researcher feels a participant is becoming distressed, they will ask the participant if they wish to have a break or discontinue the interview and will offer support. Participants will also be offered a leaflet with the contact details of support networks, or the researcher may contact the local clinical PI if necessary.

6.15.5 Qualitative Analysis

Data collection and analysis will proceed in parallel, so that analytical insights from earlier interviews can shape later data collection. Transcripts will be analysed thematically [65] to allow comparisons to be made within and across the datasets and to highlight themes and views associated with specific areas e.g. the process through which EMDR affects the emotional salience of memories. This analysis will entail transcripts being read and re-read by members of the research team to familiarise themselves with the data, identify themes and develop a coding frame. Once the coding frame has been agreed, transcripts will be imported into the software package NVivo to allow electronic coding and data retrieval. Following this, data pertaining to each code will be summarised in tables using an approach based on Framework analysis [66]. Each data set will be analysed separately before the views and experiences of therapists, patients etc are compared.

6.16 Intervention costing exercise

This study presents a unique opportunity to collect valuable information on the costs associated with EMDR, which will be of key interest to policymakers and inform future NICE decision making regarding the potential value of EMDR as a treatment for depression.

To estimate the cost of delivering EMDR in the NHS, the duration of each EMDR session and the therapist job role will be recorded on study data collection forms completed by the therapist after each session. Additionally, details of therapist supervision, including the roles of both the therapist and supervisor and the duration of supervision sessions, will be collected. Unit costs for therapists and supervisors will be derived from national sources such as the Unit Costs of Health and Social Care [67]. EMDR delivery costs will be calculated per session and per participant and presented using descriptive statistics (mean and standard deviation).

Although an economic evaluation is not funded as part of this grant, the necessary data for such an evaluation will be collected. Health-related quality of life and capability will be measured using the EQ-5D-5L and ICECAP-A, collected at baseline, 26 and 52 weeks. Resource-use data will be collected via self-report at 26 and 52 weeks, covering NHS talking therapy services, primary and secondary health care, social care, informal care, patient expenses (including travel, private and alternative care/treatments and over-the-counter medications), and time off work. With participant consent, primary care consultations and prescribed medication data will be collected via primary care medical records. Subject to further funding, cost effectiveness will be assessed in future through a cost-utility analysis, using the EQ-5D-5L to estimate quality-adjusted life years, and in a cost-effectiveness analysis, using the ICECAP-A to estimate years of full capability equivalent.

7 SAFETY RECORDING AND REPORTING

7.1 Risk Management

7.1.1 Risk Management by therapists

Trial therapists will be experienced in managing clinical risk, as this is an essential and core component of the work of mental health practitioners. Clinical risk includes risk of suicide, self-neglect, harm to self and/or others and requires practitioners to help clients manage their behaviour in relation to these sorts of risks. Trial therapists will be provided with a risk policy to promote a thorough, consistent and high standard of practice with regards to clinical risk assessment and management, to ensure that those risks are managed safely and effectively.

Whilst the patient's GP maintains overall clinical responsibility for the care of the patient, it is expected that therapists will use their clinical judgement to assess the seriousness of all risks, including risks to self and others. As part of the initial therapy session, therapists will be expected to carry out a risk assessment. Therapists will follow the Therapist Risk Policy and Procedure with regards to managing risk which may include contacting the patient's GP, their clinical supervisor or the local principal investigator with clinical responsibility (clinical PI) (or nominated deputy clinician), or other local services as appropriate. Therapists may also contact the study team to determine history of previous disclosure. Subsequent risk assessments will be triggered by PHQ9 question 9 responses collected as part of therapy, or clinical concern and will be more focused. Actions taken in response to such concerns will be clearly documented in line with the above policy.

Therapists must inform the study team of any incident (including adverse events) that result in serious harm to the participant or to others and ensure that the incident is fully documented and reported as described in section 7.8.

7.1.2 Risk policy for researchers

Should a trial researcher become concerned for the safety of a participant (for example, if the participant expresses suicidal ideation or recent self-harm at any point during participation, including during the screening call or interview) or be concerned about the safety of others, the researcher will follow the study's detailed Patient Safety and Disclosure Working Instructions for researchers, and seek advice from the local Principal Investigator with clinical responsibility (local Clinical PI) or nominated deputy clinician. If suicidal ideation is expressed, the researcher would speak to the participant about this, encourage the participant to speak to their own GP and seek permission from the patient to pass the clinical information to the GP. Should the participant refuse permission (or not respond to attempts to contact them to request permission), the local Clinical PI would assess the risk information and attempt to call the participant if necessary. The local Clinical PI would break confidentiality and pass information to the participants GP without the participant's consent if this was deemed necessary to protect the safety of the participant and only if the participant continued to decline to give permission for their GP to be contacted (or did not respond to attempts to contact them to request permission). This policy would be explained in the patient information leaflet (PIL).

7.2 Safety Definitions

Adverse Event

An adverse event (AE) is any untoward or undesirable medical occurrence in a subject receiving treatment according to the protocol. This includes occurrences which are not necessarily caused by or related to administration of the research procedures. An adverse event can therefore be any

unfavourable and unintended sign, symptom or disease temporally associated with the use of the intervention or research procedures whether or not considered to be related to the intervention/research procedures.

Adverse events that might be expected to occur at a higher rate in this group of participants include episodes of self-harm not requiring hospital admission and worsening of depression sufficient to require referral to a clinician. Although these AEs are expected, they will still be reported as data in this study. Variations in mood, including worsening of depression that does not lead to self-harm or hospitalisation, are commonly seen during therapy and would not be reported as individual adverse events. Expected events are listed in full in section 7.9.

There may be more AE reports in the intervention group as a result of their regular contact with the study team (i.e. receipt of up to 18 EMDR sessions with the study therapist, and more regular completion of the PHQ-9 and related participant safety risk assessments as part of therapy). This will be taken into consideration when interpreting the pattern of AEs.

Adverse Reaction

An adverse reaction (AR) is any undesirable experience that has happened to a subject that is suspected to be caused by the intervention.

Serious Adverse Event

A serious adverse event (SAE) is any adverse event which:

- results in death,
- is / was life threatening*,
- requires hospitalisation or prolongs an ongoing hospitalisation**,
- results in persistent or significant disability or incapacity,
- consists of a congenital anomaly or birth defect,

Other important medical events that may jeopardise the subject and may require medical or surgical intervention to prevent one of the outcomes listed above should also be classed as an SAE.

There may be more SAE reports in the intervention group as a result of their regular contact with the study team (i.e. receipt of up to 18 EMDR sessions with the study therapist, and more regular completion of the PHQ-9 and related participant safety risk assessments as part of therapy). This will be taken into consideration when interpreting the pattern of SAEs.

Suspected Serious Adverse Reaction (SSAR)

A suspected serious adverse reaction (SSAR) is any serious adverse event that is suspected (possibly or probably or definitely) to be related to the intervention.

^{*&}quot;Life-threatening" in the definition of "serious" refers to an event in which the participant was at risk of death at the time of the event; it does not refer to an event which hypothetically might have caused death if it were more severe.

^{** &}quot;Hospitalisation" is defined as an unplanned overnight stay. Note, however, that the patient must be formally admitted — waiting in outpatients or an Emergency Department would not count as hospitalisation (even though this can sometimes be overnight). Planned hospital stays would not be counted as SAEs, nor would time in hospital for "social reasons" (e.g. respite care, the fact that there is no-one at home to care for the patient). Also, if patients had a day-case operation, this would not qualify as hospitalisation. However, if a planned operation was brought forward because of worsening symptoms, this would be considered as an SAE. Hospitalisations for the purpose of the intervention are an exception to SAE reporting unless complications occur.

Non-IMP Suspected Unexpected Serious Adverse Reaction (Non-IMP SUSAR)

An SAE that occurs in a non-IMP trial and is:

- "Related" that has, possibly, probably or definitely resulted from administration of any of the research procedures, and
- "Unexpected" that is, the type of event is not listed in the protocol (or above) as an expected occurrence.

All AEs will be assessed for seriousness, causality (relatedness) and expectedness by a clinical PI or nominated deputy clinician. The clinical PI at each centre will also record whether an event is considered to be related to the participant's mental health. We will develop a detailed, study-specific standard operating procedure for reporting and recording adverse events in line with the Sponsor's requirements. This will be in place prior to the commencement of recruitment activities.

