7.9 Expected events

Expected events are clinical outcomes that routinely occur when delivering the intervention.

Expected AEs and SAEs that are a more common occurrence in this study population regardless of the study are listed below. Although these events are expected, they will still be reported in this study.

- Self-harm
- Self-harm leading to hospitalisation
- Suicide attempts
- Suicide attempts leading to hospitalisation
- Worsening of depression which requires referral to a clinician
- Worsening of depression leading to hospitalisation

All AEs will be assessed for seriousness, severity, causality and expectedness by a clinical PI or nominated deputy clinician. Relatedness to mental health will also be assessed. We will develop a detailed, study-specific standard operating procedure for reporting and recording adverse events in line with the Sponsor's requirements. This will be in place prior to the commencement of recruitment activities.

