7.10 Responsibilities

Centre Clinical Principal Investigator:

- Will check individual reports of AEs and use medical judgement in assigning seriousness, severity, causality and whether the event/reaction was expected, and whether the event was related to the participants mental health. If the local Clinical PI is not available this role will be delegated to a deputy clinician, or clinical PI from another centre.
- Ensuring that all SAEs are recorded and reported to the sponsor within 24 hours of becoming aware of the event and provide further follow-up information as soon as available.
- Ensuring that AEs and ARs are recorded and reported to the sponsor in line with the requirements of the protocol.

Chief Investigator:

 Maintain oversight of the safety of participants in the trial, including an ongoing review of the risk/benefit. A clinical PI (or deputy) will provide clinical advice to the CI in this regard.

Sponsor:

University Hospitals Bristol and Weston NHS Foundation Trust (UHBW) will monitor safety information on behalf of the Sponsor. UHBW will be given the opportunity to review the trial AE reporting SOP prior to the start of the trial.

Trial Steering Committee (TSC):

In accordance with the Trial Terms of Reference for the TSC, the group will periodically review safety data and liaise with the DMC regarding safety issues.

Data Monitoring Committee (DMC):

In accordance with the Trial Terms of Reference for the DMC, group will periodically review overall safety data to determine patterns and trends of events, or to identify safety issues, which would not be apparent on an individual case basis.

The TSC and DMC will advise the trial team on the frequency of review of individual and cumulative SAEs.

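### Protocol sections 7.2 and 7.9 conflict on whether worsening depression that needs referral, without self-harm or hospitalisation, is reported as an adverse event

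*Protocol*

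**What the plan says.** Three statements in the Protocol bear on this.

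- **Section 7.2, under Adverse Event, on expected events.** Among the AEs expected at a higher rate, it names self-harm without admission and "worsening of depression sufficient to require referral to a clinician". It then says: "Although these AEs are expected, they will still be reported as data in this study".
- **Section 7.2, the sentence that follows** (called the exemption below). Mood changes, among them "worsening of depression that does not lead to self-harm or hospitalisation, are commonly seen during therapy and would not be reported as individual adverse events".
- **Section 7.9, Expected events.** The list gives "Worsening of depression which requires referral to a clinician" and, as a separate item, "Worsening of depression leading to hospitalisation". Of the listed events it says: "Although these events are expected, they will still be reported in this study".

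Section 7.10 gives the centre's clinical principal investigator the task of handling AEs one by one: "Will check individual reports of AEs and use medical judgement in assigning seriousness, severity, causality". Sections 7.2 and 7.9 both promise a study-specific SOP for AE recording before recruitment starts. Its content is not in the document.

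**The concern.** The exemption sets its own threshold: self-harm or hospitalisation. Referral to a clinician is not part of that threshold, and there is no carve-out for it. Yet referral is the criterion that makes worsening reportable in the preceding sentences and in 7.9. Read literally, a case that meets the referral criterion and neither of the other two is both reported and not reported.

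What is at stake is how far one AE category can be interpreted. Worsening of depression accounts for two of the six expected events in 7.9, and the disputed one is the non-hospitalised item. Under section 7.7 local researchers record AEs, and under 7.10 each centre's clinical principal investigator (or a deputy) assesses them. If one centre follows the exemption and another follows 7.9, the counts reviewed by the DMC would mix two definitions.

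**Working it through.** No arithmetic applies, because the protocol gives no rate for this event and the question is whether the stated rules agree. The check applies each statement to the four kinds of worsening that the text distinguishes.

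| Case of worsening depression | 7.2, expected AEs | 7.9 list | 7.2, exemption | Do the rules agree? |
|---|---|---|---|---|
| Leads to hospitalisation | not the item named | reported | does not apply | yes, reported |
| Self-harm without hospitalisation | reported (self-harm) | reported (self-harm) | does not apply | yes, reported |
| Referral to a clinician, no self-harm, no hospitalisation | reported | reported | not reported individually | **no** |
| No referral, no self-harm, no hospitalisation | not named | not listed | not reported individually | yes, not reported |

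The conflict is confined to the third row. Three ways of dissolving it were tried against the text.

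1. **The 7.9 referral item might cover only cases that end in hospitalisation.** It cannot, because worsening that leads to hospitalisation is a separate item in the same list.
2. **Being reported as data might be a different channel from being reported as an individual AE.** No aggregate-only channel is described. Sections 7.2 and 7.9 have all AEs assessed by a clinician, and 7.10 speaks of individual reports. The phrase about reporting as data also covers self-harm without admission, and the exemption expressly leaves worsening that leads to self-harm outside its scope. The two phrases therefore appear to refer to the same channel.
3. **The SOP might settle it.** It may, but its content cannot be seen. On a literal reading, whichever rule it adopts would depart from a sentence of the protocol, and section 9.6 does not allow planned deviations.

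**The case against.** The best reply is that the exemption is about fluctuation in mood. It stands between a sentence that names referral-level worsening as reportable and a pointer to 7.9 as the full list, and 7.9 taken alone is clear. On that reading the specific item governs the general sentence, and what remains is loose drafting. This is a sensible guess at the intention, and it supports a modest severity. But the protocol does not say it, and the exemption names worsening of depression explicitly with a threshold that leaves referral out.

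It is also fair to say that the reporting flow in 7.8 is not legible in the available text and may route these cases clearly. Inconsistent counting is therefore a risk, not an established outcome.

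Two stronger readings are tempting, and the documents do not support them.

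- **That the exemption hides harm in the EMDR arm, because it refers to what is seen during therapy.** That phrase explains the exemption and does not restrict it to one arm. Usual-care participants may also be referred to talking therapy (section 5.7.6). Section 7.2 expects more AE reports in the EMDR arm because of the extra contact, and 7.7 adds EMDR appointments as a source of detection. These pull in opposite directions and the net effect is unknown. Any numerical example would only restate its assumed event rate and its assumed share of exempted cases.
- **That the trial would lose its main signal of harm.** The protocol ranks no harm as the main one. Table 2 in section 6.8 schedules the BDI-II at baseline, 26 and 52 weeks, the PHQ-9 at baseline and all six follow-ups, and a global rating of change from 8 weeks, in both arms. Deterioration remains visible in those scores, although without the assessment of causality and seriousness that an AE report carries.

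**Conclusion.** The contradiction stands, for one category only: worsening that requires referral to a clinician with neither self-harm nor hospitalisation. One statement in 7.2 and the list in 7.9 make it reportable, the next sentence of 7.2 exempts it, and no visible text decides between them. Counts of this category could differ between centres, and possibly between arms in a direction that cannot be predicted.

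Severity is moderate to low. The primary efficacy analysis and the sample size do not depend on AE counts, and worsening that leads to hospitalisation is outside the exemption. The conclusion rests on a literal reading of the sentences and on the SOP and the 7.8 flow not being available. If either already states one rule for referral-only cases, the practical risk is small, and only the protocol wording needs correcting.

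**What to change.** Reconcile the two statements in 7.2 with the list in 7.9, so that there is one reporting rule for referral-level worsening, applied identically in both arms. A small edit that would do this is to state that the 7.2 exemption covers only mood variation that meets none of the events listed in 7.9. The trial team must confirm which rule it intends. The agreed wording should then be carried unchanged into the AE SOP and the CRF, so that researchers, therapists and the assessing clinicians at all three centres work from the same definition.

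The cost is one sentence in an amendment plus alignment of the SOP and CRF. With the edit suggested, the downside is a few more AE forms to complete and assess.
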